1.3 PROTOCOL SYNOPSIS

TITLE: Combination Therapy with the Proteasome Inhibitor

Carfilzomib for the Antibody-Mediated Rejection Diagnosis in

Lung Transplantation Trial (PICARD-Lung)

Protocol number: PRO15010152

Study drug: Carfilzomib (Kyprolis®)

Phase: phase II

Patient enrollment: 30

Indication: Antibody mediated rejection after lung transplantation

Sponsor: [name]

DATE: 09/20/2018

Objectives

1: To test the hypothesis in a prospective interventional clinical trial that addition of carfilzomib to conventional therapy will result in depletion of the immunodominant DSA.

- 2: To test the hypothesis in a prospective interventional clinical trial that addition of carfilzomib to conventional therapy will result in improved or stabilized allograft function.
- 3: To test the hypothesis that lung transplant recipients with AMR have effector B cell/plasma cell populations that can be identified and characterized, and that carfilzomib alters these immune mechanisms.

Study design

Phase II, prospective, open-label, single-arm active treatment, single center pilot clinical trial of the addition of carfilzomib to conventional therapy for AMR after lung transplantation.

Outcome measures

Primary endpoint: absolute change in DSA strength, titer, and complement fixation from day 1 to day 42.

Secondary endpoints:

Absolute change in DSA strength, titer, and complement fixation from day 1 to day 90 and from day 42 to day 90

Absolute change in forced expiratory volume in 1 second (FEV1) from day 1 to day 42 and to day 90.

Presence or absence of pathologic changes consistent with AMR on transbronchial biopsy from day 1 to day 42.

Patient death at any time after day 1 attributable to AMR.

Safety endpoints:

Non-lung irreversible end-organ failure (e.g., end-stage renal disease) any time after day 1 attributable to carfilzomib.

Incidence of adverse effects (AE) requiring dose-modification any time during days 1-16.

Incidence of any AE at any time after day 1 as graded by the NIH Common Terminology Criteria for Adverse Events (CTCAE) (appendix B) criteria.

Incidence of hypogammaglobulinemia any time after day 1.

Incidence of culture-proven *de novo* infection any time after day 1.

Diagnosis of systemic inflammatory response syndrome (SIRS) any time during days 1-16

Patient death at any time after day 1 to day 90 attributable to carfilzomib.

Retrospective control group:

A 1:1 retrospective control group including lung transplant recipients from the University of Pittsburgh with Antibody Mediated Rejection will be created to describe differences in the endpoints using the CFZ-based regimen vs. historic standard of care.

Safety plan

Patients will be enrolled according to the inclusion and exclusion criteria. Patients will provide informed consent to participate in this clinical trial. In the informed consent process, patients will be educated about the purpose for carfilzomib and the potential adverse.

A study data safety monitoring board (DSMB) will be established. The DSMB will meet once yearly to review study progress, to ensure appropriate enrollment milestones are being met, and to review the adverse event reporting. The DSMB will meet on an ad-hoc basis to review any SAEs.

The DSMB may terminate the study only after at least 15 patients have been enrolled. The DSMB may only terminate the study for safety reasons in which the perceived risks of continuing to provide carfilzomib to upcoming patients who may be enrolled outweighs the potential benefit to the patient and the allograft. The DSMB may not terminate the study for any reason related to carfilzomib efficacy.

Study treatment

Carfilzomib dosing schedule: Carfilzomib will be administered on the multiple myeloma schedule consisting of 20 mg/m² on days 1 2, 8, 9, 15, and 16 (one cycle) to constitute one therapeutic cycle. On PLEX/IVIG days, carfilzomib will be given in between PLEX and IVIG to avoid inadvertent blockade of the Fcγ receptor. Premedications for carfilzomib administration will be given as follows: acetaminophen 650 mg PO, diphenhydramine 25 mg PO, ondansetron 4 mg PO, prednisone 40 mg PO or methylprednisolone 40 mg IV, all at least 30 minutes prior to and not more than 6 hours before carfilzomib, unless otherwise directed on the part of one of the investigators if believed to be in the best interests of patient care. Preinfusion hydration with a one-time bolus of 250 mL 0.9% sodium chloride will be given at least 30 minutes prior to and not more than 6 hours before carfilzomib to minimize the nephrotoxic AE. Postinfusion hydration with a one-time bolus of 250 mL 0.9% sodium chloride may be given immediately after carfilzomib to minimize the nephrotoxic AE.

Concomitant therapy and clinical practice

Conventional therapy for AMR: Therapeutic plasma exchange (PLEX) 1.5 plasma volumes replaced with 5% albumin or fresh frozen plasma for 8 sessions every-other day. Total intravenous immunoglobulins (IVIG) 100 mg/kg IV after each PLEX with the exception of the final PLEX where IVIG 500 mg/kg will be given. On day 16, if the IgG level is below 700 mg/dL, an additional dose of IVIG 500 mg/kg will be administered. If the IgG result is found to be 700ml/dL or higher, the IVIG 500mg/kg dose will not be administered. Premedications will be given for IVIG as follows: acetaminophen 650 mg PO and diphenhydramine 25 mg PO both at least 30 minutes prior to and not more than 6 hours before IVIG, unless otherwise directed on the part of one of the investigators if believed to be in the best interests of patient care. On days where IVIG and CFZ are given together, only one set of premedications will be administered. Conventional therapy requires an inpatient hospital stay. Patients will receive a tunneled PLEX catheter and peripherally inserted central catheter (PICC) inserted by interventional radiology in the routine clinical care of these patients prior to receiving any conventional or carfilzomib therapy.

Women of childbearing potential must either agree to abstain from sexual intercourse or use an effective birth control method during treatment and for an additional 30 days after the last dose of carfilzomib. Men who are sexually active with women of childbearing potential must either agree to abstain from sexual intercourse or use a condom with spermicide during treatment and for an additional 30 days after the last dose of carfilzomib, and the female partner should consider using an effective method of birth control.

Statistical methods

Data will only be analyzed in aggregate at study conclusion for the final enrolled patient on the efficacy and safety outcomes.

Descriptive statistics will be used to describe baseline and study characteristics of patients. Univariate parametric and nonparametric assessments, where appropriate, will be used to assess change from baseline in the efficacy and safety outcomes. Kaplan-Meier method will be used to describe freedom from endpoints and mortality in the patients treated with carfilzomib. Kaplan-Meier method will be used to visually represent the time to events and overall event rate in the patients in this pilot, not to compare events to any other group.

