4.1 Rationale

Carfilzomib is marketed for multiple myeloma and this IST represents an off label use of carfilzomib; thus, the criteria for phase II designation have been met. This prospective, open-label, single-arm active treatment trial will establish the rate of response to carfilzomib (in addition to conventional therapy) for AMR after lung transplantation. This information will be necessary for use in planning further larger dual-arm placebo or active therapy controlled clinical trials. This trial will enroll 30 patients at the University of Pittsburgh Medical Center. The volume of lung transplants performed and the rate of diagnosis of AMR at UPMC will allow for adequate enrollment of study patients within the 3-year study period.

The dosing strategy of carfilzomib will follow that of the multiple myeloma schedule as described below in section 5.3. This dosing strategy has been well-studied in patients with myeloma (see trial designations below) and has proven to result in an acceptable AE profile for the patients with AMR after lung transplantation. In addition, our preliminary off label experiences with this dosing strategy have yielded an acceptable AE profile in lung transplant recipients with AMR.

Trial designations:

Carfilzomib has been evaluated in 2 completed Phase 1 studies (PX-171-001 and PX-171-002), 5 completed Phase 1b/2 studies (PX-171-003, PX-171-004, PX-171-005, PX-171-006, and PX-171-008), and in 1 completed, Phase 2, expanded-access study (Study 2011-002, Carfilzomib Multiple Myeloma Expanded Access Protocol [C-MAP]) that was co-sponsored by Amgen and the Multiple Myeloma Research Foundation.

Carfilzomib is currently being evaluated in 2 ongoing Phase 1 studies (CFZ001 [Renal] and CFZ002 [Hepatic]), 5 ongoing Phase 1b/2 studies (PX-171-007, PX-171-010, 2012-002 [CHAMPION 1], 2012-003 [CHAMPION 2], and CFZ004 [small cell lung cancer]), 4 ongoing Phase 3 studies (PX-171-009 [ASPIRE], PX-171-011 [FOCUS], 2011-003 [ENDEAVOR], and 2012-005 [CLARION]), and 2 ongoing Phase 1/2 studies sponsored by Ono Pharmaceutical Co, Ltd in Japan (ONO-7057-01 and ONO-7057-02).

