4.5 Safety plan

Patients will be enrolled according to the inclusion and exclusion criteria established in section 5.3. Patients will provide informed consent to participate in this clinical trial. In the informed consent process, patients will be educated about the purpose for carfilzomib and the potential adverse effects as described in section 6.1.1. Adverse effects will be recorded and graded according to the CTCAE as described above in section 4.4.3. Serious adverse effects (SAE) will be reported timely as required and established in section 6.4.

A study data safety monitoring board (DSMB) will be established consisting of 3 members who represent non-funded non-investigators with no conflicts of interest regarding carfilzomib or the IST funding agency. The study investigators will invite qualified individuals to participate in the DSMB. The DSMB members will possess either PharmD, PhD, or MD qualifications and have a working knowledge of lung transplantation and AMR. The DSMB will be chaired by one of the three members as determined by the DSMB membership. The DSMB will meet once yearly to review study progress, to ensure appropriate enrollment milestones are being met, and to review the adverse event reporting. The DSMB will meet on an ad-hoc basis to review any SAEs.

The DSMB may terminate the study only after at least 15 patients have been enrolled. The DSMB may only terminate the study for safety reasons in which the perceived risks of continuing to provide carfilzomib to upcoming patients who may be enrolled outweighs the potential benefit to the patient and the allograft. The DSMB may not terminate the study for any reason related to carfilzomib efficacy.

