5.3.1.1 Dosage, administration, and storage

Carfilzomib dosing schedule: Carfilzomib will be administered on the multiple myeloma schedule consisting of 20 mg/m² on days 1 2, 8, 9, 15, and 16 (one cycle) to constitute one therapeutic cycle. On PLEX/IVIG days, carfilzomib will be given in between PLEX and IVIG to avoid inadvertent blockade of the Fcγ receptor. Carfilzomib will be delivered via central access IV over 30 minutes (+15 minutes); slowed to 60 minutes (+15 minutes) if infusion reactions occur.

Carfilzomib will be diluted in a total of 80 mL dextrose 5% water (D5W) for administration. Premedications for carfilzomib administration will be given as follows: acetaminophen 650 mg PO, diphenhydramine 25 mg PO, ondansetron 4 mg PO, prednisone 40 mg PO or methylprednisolone 40 mg IV, all at least 30 minutes prior to and not more than 6 hours before carfilzomib, unless otherwise directed on the part of one of the investigators if believed to be in the best interests of patient care. Preinfusion hydration with a one-time bolus of 250 mL 0.9% sodium chloride will be given at least 30 minutes prior to and not more than 6 hours before carfilzomib to minimize the nephrotoxic AE. Postinfusion hydration with a one-time bolus of 250 mL 0.9% sodium chloride may be given immediately after carfilzomib to minimize the nephrotoxic AE

Carfilzomib may be administered for 1-2 complete cycles in the study. A second cycle may be given for lack of resolution of AMR or for continued detection of DSA in the absence of allograft improvement. If > one cycle is needed, the patient must still meet the enrollment criteria prior to the second cycle, and must not have had improvement after the first cycle or have experienced regression from initial improvement to qualify for a second study cycle. If > two cycles are desired, these must be given outside of the study. If > two cycles are desired, the third cycle must not be given within 90 days of day 1 of the first cycle. If the third cycle begins within this 90 day period, this will constitute a protocol violation.

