5.10 Study discontinuation

Amgen may discontinue the study prematurely for the following reasons: the incidence or severity of AEs in this study indicates a potential serious health hazard to patients, if enrollment is sufficiently poor, or if data recording is inaccurate or incomplete.

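### The DSMB's only ground for terminating the study is risk to patients not yet enrolled, so it cannot be met after the last enrolment although carfilzomib may still be given

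*Combined protocol and SAP*

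**What the plan says.** The safety plan in the synopsis (section 1.3) and section 4.5 state the same rule. The board may terminate only for safety reasons, and the qualifying condition is that "the perceived risks of continuing to provide carfilzomib to upcoming patients who may be enrolled outweighs the potential benefit". Two further limits stand beside it: "The DSMB may terminate the study only after at least 15 patients have been enrolled" and "The DSMB may not terminate the study for any reason related to carfilzomib efficacy". Under the same sections the DSMB meets yearly, when it reviews adverse event reporting, and ad hoc for any SAE.

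Exposure continues after a patient has been enrolled. A cycle is six doses, on days 1, 2, 8, 9, 15 and 16 (section 4). Section 5.3.1.1 adds: "Carfilzomib may be administered for 1-2 complete cycles in the study". A patient considered for the second cycle must again satisfy the enrolment criteria and must have failed to improve or have regressed.

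Three other routes protect enrolled patients: dose holds and reductions for toxicity (section 5.3.1.2), removal of individual patients by the investigators (section 5.9), and discontinuation of the study by the company where "the incidence or severity of AEs in this study indicates a potential serious health hazard to patients" (section 5.10). Section 5.9 also allows patients who stop the drug early to be replaced, with no stated maximum.

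**The concern.** The condition is exclusive, and the population it names is future entrants. No other section gives the board a ground that rests on risk to patients already enrolled, or a power to halt remaining doses or second cycles. Once nobody remains to be enrolled, the condition refers to an empty group. If a safety signal emerged then, the one body set up to be free of conflicts of interest would have no stated basis for terminating a study in which drug was still being given. The company's ground in section 5.10 has no such limit: it refers to patients generally.

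This is separate from the 15-patient threshold and the bar on efficacy stopping. Removing both would leave the sentence about upcoming patients as it is.

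**Working it through.** **Inputs**
- Accrual: 10 patients per year for 3 years (section 5.13.3).
- Planned enrolment: "This trial will enroll 30 patients at the University of Pittsburgh Medical Center" (section 4.1).
- Cycle length: days 1 to 16, six doses (section 4).
- Cycles in the study: one or two (section 5.3.1.1).
- Study follow-up: to day 90 (section 5.4).
- Assumption: evenly spaced entry.
- Assumption: a second in-study cycle starts within 90 days of day 1. The protocol gives no start date for it.

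**Step 1. The plan's own figure.** 10 × 3 = 30, which agrees with the stated enrolment. It rests on accrual; there is no power calculation, and nothing here depends on one.

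**Step 2. When the ground can be used.** With the 15-patient threshold, it opens at 15/10 = 1.5 years. It closes at the last enrolment, 30/10 = 3.0 years if nobody is replaced and later if anyone is.

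**Step 3. Who is still exposed when it closes.** The spacing is 365.25/10 = 36.5 days. When patient 30 enters, the time since entry is:

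| Patient | Days since entry | Within days 1–16 | Within 90 days |
|---|---|---|---|
| 30 | 0 | yes | yes |
| 29 | 36.5 | no | yes |
| 28 | 73.1 | no | yes |
| 27 | 109.6 | no | no |

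So one patient is in cycle 1, and three are within 90 days and could be in, or become due for, a second cycle.

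**Step 4. Averages over accrual.** In cycle 1: 10 × 16/365.25 = 0.44 patients at any time. Within the 90-day window: 10 × 90/365.25 = 2.46. The second figure counts people under follow-up. It is not the number receiving drug.

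**Step 5. Doses outstanding.** If nobody needs a second cycle, up to 6 doses remain (patient 30, cycle 1). If all three have one and none of those doses has yet been given, the ceiling is 12 + 6 + 6 = 24. The true number lies between these and depends on how many patients fail to improve or regress, which the documents do not predict.

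**Step 6. The passages side by side.** Sections 1.3 and 4.5 tie the board's ground to future entrants. Section 5.3.1.1 allows dosing of existing patients to continue into a second cycle. Section 5.9 deals with enrolled patients one at a time, through the investigators. Section 5.10 covers patients in general, but the power is the company's. None of them supplies a DSMB ground that survives the last enrolment.

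**The case against.** The strongest reply concerns the accrual period. A reader might infer that harm to enrolled patients, for instance a signal in second cycles, is never a permitted reason for the board to stop. The documents do not support that. All the safety data the board sees come from treated patients, and each new entrant may receive the same one or two cycles. Toxicity seen in treated patients therefore bears directly on the risk to the next ones, and once 15 are enrolled the board can act on it. This stands, and it confines the substantive gap to the time after the last enrolment.

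A reader might also infer that independent oversight does not reach the people being exposed. That goes too far: the DSMB reviews adverse events and every SAE, and sections 5.3.1.2, 5.9 and 5.10 protect enrolled patients. What is missing is only the board's own authority to terminate.

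It can further be argued that second-cycle patients count as upcoming, since section 5.1.2 mentions them among the inclusion criteria and section 5.3.1.1 requires them to meet the enrolment criteria again. Neither section says that they are enrolled again, so this leaves an ambiguity and does not close the gap.

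Finally, replacements under section 5.9 can move the lapse beyond patient 30. That is correct, but it delays the lapse and does not remove it. The difference from section 5.10 is also not a contradiction as such, because the two powers coexist.

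**Conclusion.** The point holds in a limited form and is minor. As worded, the DSMB's only termination ground has nobody to apply to after the last enrolment, replacements included, while in-study carfilzomib may still be due. Before then the wording is narrow, but a board could reasonably work with it.

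The group affected is small: one patient in cycle 1 and roughly one to three who could receive a second cycle, with between 6 and 24 doses outstanding at most. These figures assume even accrual at 10 per year and a second cycle starting within 90 days; uneven accrual would change the count. It would be wrong to read the 2.46 patients in the 90-day window as patients on drug, or to conclude that the last patients are unprotected. The other safeguards remain in force, but none of them is a DSMB power to terminate.

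**What to change.** In the safety plan of the synopsis and in section 4.5, reword the ground so that it covers risk to patients enrolled or yet to be enrolled, and state that it remains in effect until the last in-study carfilzomib dose. The rule would then be reconciled with the second cycle in section 5.3.1.1, replacement and removal in section 5.9, and the population used in section 5.10. The change concerns the board's remit only; no dose, schedule or individual stopping rule is altered.

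The cost is one sentence in two places, made by protocol amendment. It needs no extra patients, visits or data.

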2 BACKGROUND

2.1 Background and significance

The lack of improvement in long-term allograft survival, despite improved short-term outcomes, remains the most pressing challenge in the lung transplantation field. Lung transplant recipients fare poorly relative to other solid organs with 30% incidence of chronic rejection at 2.5 years, 75% at 10 years, and only 55% of recipients surviving five years, primarily due to bronchiolitis obliterans syndrome (BOS).^{1,2} This problem is compounded by major gaps in our understanding of the immune mechanisms underlying chronic rejection.

Donor specific antibodies have a reported incidence of 10-40% in lung transplantation, and DSA both precedes and is associated with an increased risk of BOS. 3-6 Further, pre-transplant sensitization in lung transplant recipients was found to correlate with worse survival. 7 In addition to BOS, other studies have shown that DSA is associated with severe or recurrent acute cellular rejection (ACR) and lymphocytic bronchiolitis (LB), two forms of cellular rejection that are major risk factors for BOS.^{8,9} Moreover, detection of DSA with clinical antibody mediated rejection (AMR) in lung transplant recipients is difficult to treat and is associated with higher morbidity compared to ACR.20 Several studies have shown an association between the development of anti-HLA Abs and/or DSA, BOS, and decreased survival. 4.5,8-10 One such paper shows that anti-HLA antibodies are associated with ACR and lymphocytic bronchiolitis, two forms of cellular rejection that are major risk factors for BOS.8 We further investigated the relationship between DSA and BOS in 445 LT recipients at the University of Pittsburgh, over a 7-year period (2003-2010). As shown in figure 1, DSA was associated with significantly reduced freedom from BOS and decreased survival in LT recipients followed for 3.4 ±1.6 yrs. Furthermore, we found that the risk of BOS was significantly increased in the DSA+ group compared to the non-DSA group using a Cox proportional hazards model (HR 6.32; 95% CI 4.34-9.18; p<0.001).

[figure not shown]

Figure 1: Freedom from BOS and Mortality in DSA vs. no DSA in lung transplantation recipients from UPMC.

Moreover, the presence of high-grade BOS (BOS stage 2 or 3) was significantly increased in the DSA+ versus the no-DSA group. Together, these data indicate that development of DSA is significantly associated with accelerated, high-grade BOS in lung transplantation recipients, along with diminished patient survival. Thus, DSA and AMR are emerging as a formidable challenge in lung transplantation.

Contrary to lung transplantation, the evidence and agreement supporting the AMR are robust in renal transplantation. That said, the majority of the principles learned in renal transplantation are applicable to the lung. One such lesson is the impact of functional phenotype of DSA, ergo whether the DSA is able to fix complement at peripheral blood concentrations in vitro. A novel solid phase Luminex single antigen bead (SAB) assay was developed which allows the detection of complement fixing HLA antibodies with high sensitivity and specificity (Luminex-C1q). 11 In renal transplantation, several small studies suggest that C1q-binding DSA correlates with transplant glomerulopathy (TG) and irreversible renal allograft failure. ¹² In particular, persistent complement binding DQ-specific DSA is associated with a 30% lower 5-year allograft survival. In a recent large study in a cohort of 1016 renal transplant recipients, co-authored by co-investigator [name], the presence of DSA and C1q-binding donor-specific anti-HLA antibodies at 1 year, or at the time of acute rejection within 1 year, was correlated with 5 year allograft survival (Figure 2). Patients with complement-binding DSA had significantly reduced 5-year allograft survival (54%) compared to those with non-complement binding DSA (93%). C1g binding of de novo DSA was independently associated with graft loss whether it was detected in samples taken at the one year protocol biopsies or in samples taken during acute rejection in the first-year post-transplantation.

[figure not shown]

Figure 2: Kaplan-Meier curve of probability of graft survival based on DSA phenotype. Panel A: conventional Luminex-IgG vs. no DSA. Panel B: Luminex-IgG and C1q vs. no DSA.

